## 13. STATISTICAL CONSIDERATIONS

### 13.1 Mycosis Fungoides/Sézary Syndrome (Treatment group 1)

#### 13.1.1 Study Design/Endpoints

##### 13.1.1.1 *Primary Objective*

To assess the overall response rate (ORR) of MK-3475 (pembrolizumab) and IFN-gamma (Actimmune®) combination immunotherapy in subjects with previously treated Mycosis Fungoides or Sézary Syndrome.

In this single stage phase II open label trial, we will have an interim futility analysis. When 12 patients have been followed for 6 months, we will perform the interim futility analysis. If ORR is less than 33% (4 or less CR+PR), the trial will stop and we will accept the null that combination therapy is no better than monotherapy. Otherwise, trial will continue until 30 patients accrue. If ORR is at least 57% (17 or

more CR+PR) at the final analysis, we will accept the alternative that combination therapy is significantly better than monotherapy.

**Hypothesis:** Administration of MK-3475 (pembrolizumab) and IFN-gamma (Actimmune®) as a combination immunotherapy regimen to subjects with previously treated Mycosis Fungoides or Sézary Syndrome will result in a clinically meaningful ORR that is an improvement over the ORR of MK-3475 (pembrolizumab) or IFN-gamma as monotherapy.

#### 13.1.1.2 *Secondary Objectives*

To explore the safety/tolerability and clinical activity of MK-3475 (pembrolizumab) and IFN-gamma (Actimmune®) in subjects with previously treated Mycosis Fungoides or Sézary Syndrome with respect to the following secondary endpoints:

##### *Safety and tolerability*

Interim safety review based on distinct patient SAE's following the first 3 doses of pembrolizumab (10 weeks of therapy) that are attributable to study drugs; We will allow 10% or less of patients to develop study drug related SAEs. If 4 or more patients amongst the first 12 evaluable patients for toxicity at pre-C4 (week 10) have experienced study drug related serious adverse events (SAEs), we will conclude that the combination immunotherapy regimen is too toxic and accrual will stop. If accrual is not stopped for either interim futility or safety reasons, a final safety evaluation will be conducted based on the percentage of the 30 patients who have experienced SAEs. We will consider the safety profile being acceptable if less than 6 patients have experienced study drug related SAEs. Otherwise, we will evaluate the tradeoff between safety and efficacy benefits based on the magnitude of ORR improvements.

##### *Time to response (TTR)*

##### *Duration of response (DOR)*

is defined as the time interval between the date of first response (CR/PR) and the date of progression.

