**Response in Skin\***

Complete response (CR)	100% clearance of skin lesions #
Partial response (PR)	50-99% clearance of skin disease from baseline without new tumors (T 3 ) in subjects with T 1 , T 2 or T 4 only skin disease
Stable disease (SD)	<25% increase to <50% clearance in skin disease from baseline without new tumors (T 3 ) in subjects with T 1 , T 2 or T 4 only skin disease
Progressive disease (PD) †	(1) >25% increase in skin disease from baseline or (2) New tumors (T 3 ) in subjects with T 1 , T 2 or T 4 only skin disease or (3) Loss of response: in those with CR or PR, increase of skin score of greater than the sum of nadir plus 50% baseline score
Relapse	Any disease recurrence in those with CR

\*Based on mSWAT score.

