Local reading (investigator assessment with site radiology reading) will be used to determine subject eligibility and for subject management. Radiologic scans may be sent to a central vendor for evaluation.

11.1.1.7 *Duration of Response*

Duration of overall response: The duration of overall response is measured from the time measurement criteria are met for CR or PR (whichever is first recorded) until the first date that recurrent or PD is objectively documented (taking as reference for PD the smallest measurements recorded since the treatment started).

The duration of overall CR is measured from the time measurement criteria are first met for CR until the first date that PD is objectively documented.

Duration of stable disease: SD is measured from the start of the treatment until the criteria for progression are met, taking as reference the smallest measurements recorded since the treatment started, including the baseline measurements.

ORR12: Patients who have a response duration of at least 12 months.

11.1.1.8 *Progression-Free Survival*

PFS is defined as the duration of time from start of treatment to time of progression or death, whichever occurs first.

11.1.1.9 *Response Review*

No review of response rate is contemplated. Investigator determined responses will be chronicled.

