##### *Progression-free survival (PFS)*

is defined as the time from enrollment to PD or death, whichever occurs earlier, based upon investigator assessment. Patients without documented PD/death will be censored at the last disease assessment date.

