##### *Event-free survival*

(EFS events defined as termination due to toxicity, initiation of next significant treatment, progressive disease, or death of any cause)

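### Group 1 gives conflicting end dates for response duration, and Section 13 read literally does not count a relapse after CR that stays below the PD threshold

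*Combined protocol and SAP*

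**What the plan says.** **Response categories.** Section 11.1.1.6 gives Relapse its own row, separate from PD, in the skin, node, blood and visceral tables and in the global score. In skin, Relapse is "Any disease recurrence in those with CR". The third route to skin PD is "Loss of response: in those with CR or PR, increase of skin score of greater than the sum of nadir plus 50% baseline score".

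**Duration of response.** Section 11.1.1.7 runs overall response "until the first date that recurrent or PD is objectively documented". The next paragraph has duration of CR "measured from the time measurement criteria are first met for CR until the first date that PD is objectively documented". Section 13.1.1.2 (and 1.2.1.3) says that DOR "is defined as the time interval between the date of first response (CR/PR) and the date of progression".

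**PFS and EFS.** In Section 13.1.1.2, PFS "is defined as the time from enrollment to PD or death, whichever occurs earlier, based upon investigator assessment". For EFS it gives "EFS events defined as termination due to toxicity, initiation of next significant treatment, progressive disease, or death of any cause". Neither mentions Relapse.

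**Censoring.** The efficacy analysis table in Section 13.1.1.3 censors DOR and PFS at last follow-up or at new significant therapy. For ORR12, new significant therapy before 12 months is a failure.

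**The concern.** For a complete responder whose disease comes back at a low level, the plan gives two end dates for the same response. The first sentence of 11.1.1.7 ends it at the recurrence. The wording in Section 13, and the duration-of-CR sentence in 11.1.1.7, can be read as letting it run until PD.

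The protocol foresees this situation: it allows treatment to stop after CR and to restart on recurrence (5.10, 11.1.1). An analyst would have to choose a reading, possibly after seeing the data, and the literal Section 13 reading can only lengthen DOR, ORR12, PFS and EFS.

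**Working it through.** The plan states no figure on this point, so the check compares definitions and then sizes the gap.

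**1. Relapse against PD after CR (tables in 11.1.1.6)**

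| Compartment | Relapse | PD routes that matter after CR | Relapse but not PD |
|---|---|---|---|
| Skin | any recurrence | score above nadir + 50% of baseline; new T3 tumors in patients with T1, T2 or T4 only | score above 0 and up to 50% of baseline, no such tumors |
| Blood | B1 or higher | B0 to B2; above 1000 neoplastic cells/µL after CR if B1 or B2 at baseline | B1 meeting no PD route |
| Nodes | new node >1.5 cm | new node proven N3; SPD up by more than 50% | new node >1.5 cm not proven N3, SPD routes not met |
| Viscera | new organ | new organ | none |

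The nodal gap assumes that the N3 condition governs both size alternatives in the PD row. If it governs only the smaller nodes, that gap closes.

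**2. Width of the skin gap.** After CR the nadir mSWAT is 0.
- PD by loss of response: score > 0 + 0.5 × baseline.
- PD by increase from baseline: score > 1.25 × baseline, which is always higher, so the first governs.
- For baselines of 20, 50, 80, 120 and 200, recurrences up to 10, 25, 40, 60 and 100 are Relapse but not PD on these routes.

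**3. What happens to a relapse in the gap**
- First sentence of 11.1.1.7: DOR ends.
- Section 13 read literally: DOR and PFS continue. If new significant therapy then starts, both are censored and the relapse is never counted.
- EFS: no event until a next significant treatment, PD, toxicity termination or death. Whether restarting study drug is a next significant treatment is not stated.

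**4. Effect on one patient (illustration).** Assume skin relapse 6 months after first response, PD reached one, two or three global assessments later, and no new therapy meanwhile. Assessments every 4 cycles are 12 weeks, or 2.76 months, apart.
- DOR under the first sentence of 11.1.1.7: 6 months.
- DOR under literal Section 13: 6 + 2.76 = 8.8, 6 + 5.52 = 11.5, or 6 + 8.28 = 14.3 months. Only the last also counts toward ORR12.

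**5. Effect on ORR12.** With 30 evaluable patients, one patient is 1/30 = 3.3 points. With c complete responders, of whom a share s relapse before 12 months without PD or new significant therapy by then, the excess is c × s / 30.
- The prior monotherapy trial (2.4.3) had 1 CR in 24 patients and 9 responders: 30 × 1/24 = 1.25 CRs in 30, or 17 × 1/9 = 1.9 among 17 responders.
- For s from 0.25 to 1: c = 1 gives 0.8 to 3.3 points; c = 2 gives 1.7 to 6.7 points.
- If the combination produced c = 5 (assumption, not supported by a rate in the documents): 4.2 to 16.7 points.

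**6. Design figures.** The stopping and success rules in 13.1.3.1 count CR + PR only. Exact binomial calculation of those rules gives type I error 2.15% and power 86.6% (stated 2% and 87%). Neither uses a duration.

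**The case against.** A reader might infer that no relapse after CR is an event in Section 13. The documents do not support that. Relapses that meet a PD route are already events: loss of response, B0 to B2, new T3 tumors in T1, T2 or T4 patients, or a new organ. EFS also catches relapses that lead to a next significant treatment, though late.

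The word progression in the DOR definition may be loose. Sections 11.1.1 and 11.1.1.3 describe the same retreatment situation, one as disease recurring and the other as the subject progressing. Section 11.1.1.7 is the detailed text on duration and also defines ORR12, so an analyst could reasonably take its first sentence as governing. This stands: an upward bias is possible, not established. It does not remove the conflict, because the CR sentence in 11.1.1.7 and the PFS and EFS definitions name PD specifically.

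A reader might also put the CR count at 3 or more by adding the two near-global CRs of the prior trial. Section 2.4.3 classes those as PRs, so they could not have a Relapse. Eight of that trial's nine responders were PRs.

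Finally, PD or death is a coherent PFS definition, and counting Relapse has a complication. Section 11.1.1.3 requires confirmation after 4 weeks for response and PD but says nothing about Relapse, in a trial that expects immune-related skin flares (5.9). That objection stands, and the fix has to deal with it.

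**Conclusion.** The conflict is real and should be settled before analysis. Response duration has two written end dates in Group 1, and PFS and EFS do not say whether Relapse counts. The literal Section 13 reading leaves sub-PD relapses in skin, blood and possibly nodes uncounted, and any resulting bias favours durability.

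The size rests on the number of CRs. At the prior trial's rate it is one or two patients, each worth 3.3 points of ORR12 under the conditions in step 5. It would grow with a higher CR rate, which the documents do not predict. Only secondary endpoints are affected; primary ORR, sample size, type I error and power do not change.

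**What to change.** Write one rule and use it in 1.2.1, 11.1.1.7 and 13.1.1.2:
- DOR, duration of CR and the response duration behind ORR12 end at first PD or Relapse by global score. This matches the first sentence of 11.1.1.7.
- The disease event in PFS and EFS is the same.
- Replace the PD-only sentence for duration of CR in 11.1.1.7.
- State whether the 4-week confirmation in 11.1.1.3 also applies to Relapse.
- Report the PD-only version as a sensitivity analysis.

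The cost is wording in these sections. The scheduled assessments already supply the data. Reported durations may be slightly shorter.

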##### *Progression-free survival (PFS)*

is defined as the time from enrollment to PD or death, whichever occurs earlier, based upon investigator assessment. Patients without documented PD/death will be censored at the last disease assessment date.

##### *Event-free survival*

(EFS events defined as termination due to toxicity, initiation of next significant treatment, progressive disease, or death of any cause)

##### *ORR12*

Percentage of all patients who have a response duration of at least 12 months (ORR12)

**Hypothesis:** Combination immunotherapy of MK-3475 (pembrolizumab) and IFN-gamma (Actimmune®) will have acceptable safety/tolerability profile in previously treated Mycosis Fungoides/Sézary Syndrome population and meaningful clinical activity will be reflected in other clinical outcome parameters including DOR, PFS, EFS and ORR12.

#### 13.1.1.3 *Exploratory Objectives*

To investigate the relationship between the following putative biomarkers for combination immunotherapy of MK-3475 (pembrolizumab) and IFN-gamma (Actimmune®) and clinical outcomes (as measured by safety/tolerability and ORR, DOR, PFS, EFS) in subjects with previously treated Mycosis Fungoides/Sézary Syndrome, including tumor/microenvironment (PD-1/PD-L1/PD-L2 expression, CTLs, Tregs, macrophages, DCs; nanostring gene expression profile), systemic immune response (flow cytometry, CyTOF, Luminex multiplexed cytokine profile), and molecular/genomic immune correlates (exome sequencing, high throughput sequencing (HTS) for TCR).

**Hypothesis:** The putative biomarkers and immune regulators tested will be related to clinical response induced by combination immunotherapy of MK-3475 (pembrolizumab) and IFN-gamma (Actimmune®) and will help define actionable causes of not achieving CR.

The primary and key secondary endpoints, primary analysis population, and statistical methods that will be employed for the efficacy analyses are presented in the Table below.

**Summary Analysis Strategy for Efficacy Endpoints**

Endpoint/Variable (Description, Time Point)	Statistical Method	Analysis Population	Missing Data Approach
Primary:			
Overall response rate (ORR) per global assessment of Mycosis Fungoides and Sézary Syndrome (confirmed & investigator assessed)	Binomial proportion	Evaluable population as defined	Subjects without any efficacy evaluation will be excluded; if one compartment is missing data, that compartment will be considered non-response
Secondary:			
Time to Response (TTR)	Simple statistics	All responders	Non-responders are excluded in analysis
Duration of Response (DOR)	Kaplan-Meier method	All responders	Non-responders are excluded in analysis; censored at last f/u or start of new significant therapy
Progression-free survival	Kaplan-Meier method	All efficacy or safety evaluable patients	Censored at last f/u or start of new significant therapy

Endpoint/Variable (Description, Time Point)	Statistical Method	Analysis Population	Missing Data Approach
Event-free survival	Kaplan-Meier method	All efficacy or safety evaluable patients	Event is defined by early termination due to toxicity, start of new significant therapy, PD, or death of any cause
Rate of overall response duration beyond 12 months (ORR12) per global assessment of Mycosis Fungoides and Sézary Syndrome (confirmed & investigator assessed)	Binomial distribution	Evaluable DOR beyond 12 months for evaluable population.	Subjects without any efficacy evaluation will be excluded; The ORR12 is the proportion of ORR times conditional probability of DOR beyond 12 months. If one compartment is missing data, that compartment will be considered non-response. Censored at last f/u. Start of new significant therapy before 12 months will be considered as failures.

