- 3.1.1.5 Have measurable disease based on mSWAT (definition provided in Appendix). Tumor lesions situated in a previously irradiated area are considered measurable if progression has been demonstrated in such lesions.
- 3.1.1.6 Have a performance status of 0 or 1 on the ECOG Performance Scale.
- 3.1.1.7 Patients must have normal organ and marrow function (all screening labs should be performed within 10 days of treatment initiation) as defined below:

System	Laboratory Value
Hematological	
Absolute neutrophil count (ANC)	$\geq 1500/\text{mcL}$
Platelets	$\geq 100\,000/\text{mcL}$
Hemoglobin	$\geq 9\text{ g/dL}$ or $\geq 5.6\text{ mmol/L}$
Renal	
Creatinine OR measured or calculated creatinine clearance (CrCl) a,b	$\leq 1.5 \times \text{ULN}$ OR $\geq 60\text{ mL/min}$ for patient with creatinine levels $>1.5 \times$ institutional ULN
Hepatic	
Total bilirubin	$\leq 1.5 \times \text{ULN}$ OR Direct bilirubin $\leq \text{ULN}$ for patients with total bilirubin levels $>1.5 \times \text{ULN}$
AST (SGOT) and ALT (SGPT)	$\leq 2.5 \times \text{ULN}$ OR $\leq 5 \times \text{ULN}$ for patients with liver metastases

a Creatinine clearance (CrCl) should be calculated per institutional standard.

b Glomerular filtration rate (GFR) can also be used in place of creatinine or CrCl.

- 3.1.1.8 The effects of MK-3475 (pembrolizumab) and Interferon-gamma on the developing human fetus are unknown. For this reason and because anti-PD-1agents and Interferons may be teratogenic, women of child-bearing potential and men must agree to use adequate contraception (hormonal or barrier method of birth control; abstinence) before study entry and for the duration of study participation.
- 3.1.1.9 Female patients of childbearing potential must have a negative urine or serum pregnancy test within 72 hours before receiving the first dose of study medication. If the urine test is positive or cannot be confirmed as negative, a serum pregnancy test will be required.
- 3.1.1.10 Female patients of childbearing potential ([Section 5.7](#)) must be willing to use an adequate method of contraception as outlined in [Section 5.7](#) Contraception and Pregnancy, for the course of the study through 120 days after the last dose of study medication.
- Note:** Abstinence is acceptable if this is the usual lifestyle and preferred contraception for the patient.

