#### ***Disease Assessments***

- All patients: mSWAT at screening, pre-IFN-gamma lead-in, C1D1, C2D1, then every other cycle thereafter, and for CR/PR, PD or EOT, and in the event of a Skin Flare Reaction.
- Presence of extracutaneous disease at enrollment: Sezary flow at pre-IFN-gamma lead-in, C2, C6, C10, then every 4 cycles and in the event of a Skin Flare Reaction; Imaging at screening, C5-6, C9-10, (before MK-3475 (pembrolizumab) is administered at cycle 6, and 10) then every 4 cycles, both Sezary flow and imaging are performed to confirm PR and/or CR, when suspect PD and at EOT.
- Absent extracutaneous disease at enrollment: Imaging at screening, Sezary flow at pre-IFN-gamma lead-in, then both are performed to confirm PR and/or CR, when suspect PD, at EOT and in the event of a Skin Flare Reaction.

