##### 11.1.1.1 *Definitions*

Evaluable for toxicity. All patients will be evaluable for toxicity from the time of their first treatment with Interferon-gamma (given first as run-in before MK-3475 (pembrolizumab)).

Evaluable for objective response. As described above patients enrolled in this trial may not have disease that is measurable by CT and/or PET/CT however they can still

be objectively evaluated for disease response using parameters unique to Mycosis Fungoides/Sézary Syndrome.

11.1.1.2 *Disease Parameters: N/A*

11.1.1.3 *Tumor Imaging and Assessment of Disease*

The primary outcome is antitumor effect. Definitions for global response, CR, PR, PD, and SD (in skin/LN/viscera/blood) are detailed here.

*Measurement Methods*

- Skin: mSWAT.
- Lymph nodes: CT or PET/CT (Olsen criteria).
- Viscera: CT or PET/CT (Olsen criteria).
  - If using a PET/CT the CT should be of diagnostic quality
- Blood: Flow cytometry.

The skin compartment is the target of primary efficacy assessment, however in those subjects with extracutaneous disease, all involved compartments will be assessed separately and a global response will be determined.

Clinical response in the skin compartment will be assessed according to changes in the modified Severity-Weighted Assessment Tool (mSWAT) [Appendix E] and documented as SD, PR, complete clinical response, or PD as defined below. The response in the lymph node compartment will be assessed by IWG criteria, in blood by flow cytometry, and global response will be assigned adhering to the consensus criteria below. All objective response (PR or CR) and progression (PD) must be confirmed after 4 weeks. Digital copies of mSWAT photographs will be retained at sites for quality assurance or secondary review purposes.

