##### 13.1.5.2 *Evaluation of Response*

All patients included in the study must be assessed for response to treatment, even if there are major protocol treatment deviations or if they are ineligible. Each patient will be assigned one of the following categories: (1) complete response, (2) partial response, (3) stable disease, (4) progressive disease, (5) early death from malignant

disease, (6) early death from toxicity, (7) early death because of other cause, or (9) unknown (not assessable, insufficient data). [Note: By arbitrary convention, category 9 usually designates the “unknown” status of any type of data in a clinical database.]

All of the patients who met the eligibility criteria (with the possible exception of those who received no study medication) should be included in the main analysis of the response rate. Patients in response categories 4-9 should be considered to have a treatment failure (disease progression). Thus, an incorrect treatment schedule or drug administration does not result in exclusion from the analysis of the response rate. Precise definitions for categories 4-9 will be protocol specific.

All conclusions should be based on all eligible patients. Subanalyses may then be performed on the basis of a subset of patients, excluding those for whom major protocol deviations have been identified (e.g., early death due to other reasons, early discontinuation of treatment, major protocol violations, etc.). However, these subanalyses may not serve as the basis for drawing conclusions concerning treatment efficacy, and the reasons for excluding patients from the analysis should be clearly reported. The 95% confidence intervals should also be provided.

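### Group 1's primary response rate has two unreconciled denominator rules, and the plan does not define the evaluation that separates them

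*Combined protocol and SAP*

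**What the plan says.** The sentence that closes Section 13.1.1.3 says that the "primary analysis population, and statistical methods that will be employed for the efficacy analyses are presented in the Table below". In that table, the primary ORR row names an evaluable population, said to be defined, and handles missing data as follows: "Subjects without any efficacy evaluation will be excluded; if one compartment is missing data, that compartment will be considered non-response". The ORR12 row carries the same exclusion, although Section 1.2.1.6 defines ORR12 as a percentage of all patients.

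Section 13.1.5.2 covers the same group and endpoint. All patients who met the eligibility criteria, with a possible exception for those who received no study drug, "should be included in the main analysis of the response rate. Patients in response categories 4-9 should be considered to have a treatment failure". Category 9 is "unknown (not assessable, insufficient data" in the plan's words. The section adds: "All conclusions should be based on all eligible patients". It bars subset analyses from serving as the basis for efficacy conclusions. It also says that exact definitions of categories 4 to 9 are left to the protocol.

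The nearest text to a definition of evaluability is in Section 11.1.1.1: "Evaluable for objective response. As described above patients enrolled in this trial may not have disease that is measurable by CT". It goes on to say that such patients can still be evaluated by other means, but it sets no minimum assessment.

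On how often disease is assessed, Section 3.1.1.5 requires patients to "Have measurable disease based on mSWAT (definition provided in Appendix", and Section 5.1.1 schedules "All patients: mSWAT at screening, pre-IFN-gamma lead-in, C1D1, C2D1, then every other cycle thereafter, and for CR/PR, PD or EOT". Footnotes to the Section 10.1 calendar place the first global assessment at Cycle 6, which the calendar shows as weeks 16-18.

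**The concern.** The table and Section 13.1.5.2 each claim to set the population for the main response-rate analysis, and nothing in the document says which prevails. The patient at issue is eligible, has been dosed, and has no efficacy evaluation of the kind the table has in mind. The table removes that patient from the denominator; Section 13.1.5.2 keeps the patient as a failure.

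Such a patient cannot be a responder, so removal either raises the ORR or leaves it unchanged. The trial is single-arm and open-label, and response is assessed by the investigator. The denominator of the headline result should therefore be settled before the data are seen.

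**Working it through.** **1. When the two rules differ.** It depends on what counts as any efficacy evaluation.

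- If the pre-dose mSWAT counts (screening and before the IFN-gamma lead-in), every dosed patient assessed on schedule has an evaluation. The table then drops only never-dosed patients, whom Section 13.1.5.2 also allows to be left out. The rules agree.
- If a post-baseline evaluation is meant, a dosed patient who leaves without one is treated differently by the two rules.
- If a global evaluation is meant, which is how the table describes the endpoint, patients who leave before Cycle 6 without a full end-of-treatment assessment are exposed as well.

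**2. Reproduce the stated design.** Inputs from Section 13.1.3.1: null 37%, alternative 65%, stop at 4 or fewer of 12, success at 17 or more of 30.

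P(success) = Σ over x = 5 to 12 of P(X₁ = x; n = 12, p) × P(X₂ ≥ 17 − x; n = 18, p).

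| Quantity | Recomputed | Stated |
|---|---|---|
| Type I error (p = 0.37) | 2.15% | 2% |
| Power (p = 0.65) | 86.6% | 87% |
| Interim stop, null | 52.5% | 52% |
| Interim stop, alternative | 2.55% | 2% |

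**3. Counts or percentages?**

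- Final: 17/30 = 56.7%, so a literal 57% of 30 needs 0.57 × 30 = 17.1, hence 18 responders. That gives 0.86% and 77.6%, which do not match the stated figures. So 57% is a rounded label for 17/30.
- Interim: 4/12 = 33.3% is not below 33%. A literal reading would stop only at 3 or fewer, with a null stopping probability of 29.5% instead of 52%. The count is what was computed. The printed inequality is wrong, and this is not a matter of rounding.
- The interim summary table after Section 13.1.1.4 sets the futility look on 12 patients enrolled and dosed, with no exclusion for evaluability.

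**4. Effect on the reported result.** The documents give no expected number of unevaluated patients, so the numbers below are assumptions. Intervals are Clopper-Pearson 95%.

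| Assumed data | Table rule | 13.1.5.2 rule |
|---|---|---|
| 1 of 30 unevaluated, 17 responders | 17/29 = 58.6% (38.9-76.5%) | 17/30 = 56.7% (37.4-74.5%) |
| 1 of 30 unevaluated, 16 responders | 16/29 = 55.2% (35.7-73.6%) | 16/30 = 53.3% (34.3-71.7%) |
| 2 of 30 unevaluated, 16 responders | 16/28 = 57.1% (37.2-75.5%) | 16/30 = 53.3% (34.3-71.7%) |

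In the last row the interval excludes the 37% null under one rule and includes it under the other. Both miss the count of 17.

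**5. Bound if the percentage were applied to evaluable patients.** Each patient is a responder with probability 0.37, unevaluable with assumed probability u, and otherwise an evaluable non-responder. The interim stays a count, and final success requires responders/evaluable to reach the cut.

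| u (assumed) | Type I error, cut 0.57 | Type I error, cut 17/30 |
|---|---|---|
| 1/30 | 2.0% | 2.6% |
| 5% | 2.6% | 3.1% |

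**6. Power under the 13.1.5.2 rule.** The 86.6% requires 65% to be the rate among all patients. If 65% applies only to evaluable patients and k others count as failures, 17 responders must come from 30 − k patients. Power is then 81.6% for k = 1 and 75.0% for k = 2, taking the 12 interim patients as evaluable.

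**The case against.** Section 13.1.5.2 is written in terms of what should be done and leaves the exact meaning of categories 4 to 9 to the protocol, so the table might be read as supplying it. That would need text narrowing category 9, and there is none. The point softens the conflict without resolving it.

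The table excludes only patients without any evaluation, and mSWAT is done before dosing. Read literally, it drops no dosed patient who has that assessment. This stands. A reader might infer that the two denominators must conflict, but the documents support only that they do so under some readings of an undefined term.

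A reader might also infer that the trial could be declared a success because of the exclusion, since 16/28 = 57.1% passes a 57% cut. The stated error rates do not support that: they come from counts on 12 and 30, and 16 responders miss the count. The type I figures in step 5 are therefore only a bound, and one of them (2.0%) lies below the count rule's own 2.15%.

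The consequence is small. With 16 responders, one unevaluated patient is not enough to lift the lower limit above 37% (35.7%), and two lift it only to 37.2%. Frequent mSWAT makes even two uncertain.

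Finally, a reader might see the same contradiction in Group 2, whose table after Section 13.2.1 repeats the exclusion. Section 13.1.5.2 belongs to Group 1, and Section 13.2 has no competing rule, so Group 2 shows no contradiction.

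**Conclusion.** The point holds in limited form. Group 1's primary ORR has two denominator rules that the plan does not reconcile, and the term that would decide whether they differ is undefined. If the counts govern, as the stated 2% and 87% show they were meant to, neither go/no-go nor type I error is affected.

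What is open is the reported ORR and its confidence interval, which the exclusion can only move upward. The shift is 1.9 percentage points for 17 responders with one patient unevaluated (58.6 − 56.7) and 3.8 points for 16 responders with two (57.1 − 53.3). Those numbers of unevaluated patients are assumptions; the assessment schedule suggests few.

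**What to change.** - In the ORR and ORR12 rows of the Group 1 efficacy table, replace the exclusion with the Section 13.1.5.2 rule: all eligible patients who received at least one dose of either drug, with those lacking a post-baseline efficacy evaluation counted as non-responders. Leave the compartment response criteria unchanged.
- State that the decision rules are the counts: stop at 4 or fewer of 12, success at 17 or more of 30. Say that 57% is a rounded label for 17/30, and correct the interim wording that puts the threshold below 33%.
- Name one denominator for the counts, and say how a dosed patient later found ineligible is handled in it. The interim table refers to dosed patients and Section 13.1.5.2 to eligible ones.
- Report evaluable-only ORR with its 95% interval as a sensitivity analysis.
- Using the same wording in the Group 2 table is optional, for consistency only.

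The cost is wording, with no added patients, visits or procedures. The reported ORR may be slightly lower. The plan should also acknowledge that 87% power assumes 65% is the all-patient rate; otherwise power is about 82% with one unevaluable patient and 75% with two.
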